Effectiveness of Extra- oral Suction Comparing to Other Suction in Reducing Particles Matter and Bioaerosol in Dental Clinic, Randomized Clinical Trial.

NCT05848245

September 15, 2022

[name]

Supervised by

[name], [name], [name]

Content table

.1	Abstract in English	3
.2	Introduction	4
	Background 3.1	4
	Rational of research 3.2	5
	Objective 3.3	5
	MATERIAL AND METHODS .4	5
	Study design 4.1	5
	Intervention devices 4.2	5
	Intervention groups 4.3	6
	Study area and setting 4.4	6
	Assessment 4.5	6
	Study participants 4.6	7
	Sample size 4.7	7
	Sampling technique 4.8	7
	Inclusion and exclusion criteria 4.9	7
	Variables and Data collection 4.10	7
	Statistical consideration 4.11	9
	Ethical consideration 4.12	9
	Limitation and strength 4.13	9
	Devices and setting figure .5	10
.6	References	12

1. Abstract in English

Aerosol particles generated when using dental instrument such as ultrasonic and high air driven handpieces, this aerosol is mixture of blood, saliva, infectious agents, and dental materials. Inhaler dust that range between PM2.5 to PM10 could transferred to the human lung's terminal bronchioles and alveoli that cause a harm effect.

The aim of this study to assess the effectiveness of different dental suction devices that could be contributed to decrease risk of particles count, Bacterial and fungal that arising from patient mouth to indoor air dental clinic

This is a randomized clinical trial will be conducted in three different places: educational hospital, public hospital, and private clinic. In each place 40 subject will be recruited. Measurement including particles count and microorganism will be taken before 15 minutes and during of scaling and prophylaxis procedure to measure particles count, oral bacteria, fungus, and microbial air. In this study will be compared between four intervention groups; Group A with high and low suction only, Group B using dry shield suction and low section, Group C using extra-oral suction with high and low suction, and Group D using dry shield suction and extra-oral suction and low section. Difference between each categorical groups and particle, oral bacterial, fungus, and microbial air concentration will be tested using two-way ANOVA test or one way ANOVA test. Statistical analysis will be carried using STATA version 13.

2. Introduction

2.1 Background

Aerosols described as any fluid and solid particles dropped in the air. Any particles less than 50 micrometer in diameter could be suspended into air for extended period before rest on environmental surfaces or enter respiratory tract(1). Bioaerosol Are a complex mixture of airborne particles of biological origin such as bacteria, viruses, and fungus.

In dental clinic, dental team are exposed to infectious droplet through a direct contact with body fluid of patient, contact with environmental surfaces or instrument(2). Dental aerosol might be not easily to measure. However, many studies assess the amount of bacteria using bacteria growth media such as blood agar culture(1). In addition, particle number concentrations are considered to more closely indicate the health exposure risk to characterize cleanroom. Particles in the range of 0.5–10 μm diameter can be inhaled and held on the human lung's terminal bronchioles and alveoli(3). Dental instruments and procedure generate varies air-borne contamination amount, the highest bacterial growth was produced by ultrasonic scaler, followed by the air-driven high-speed handpiece, the air polisher and various other instruments such as the airwater syringe and prophylaxis angles(4-6). In addition, one of study in vitro was found the high amount of aerosol and spatter generated from ultrasonic scalar if used without cooling and presence of small amounts of liquid placed at the operative site to mimic blood and saliva (7)

Using personal protective barrier would be prevented spatter droplets but particles which is less than 50 micrometer that consist of infectious agent has the potential to enter the respiratory tract through leaks in masks (8). The exact hazard effects of dental aerosol not possible to recognize currently however the probable spread of infection should be minimized and eliminated (1).

Nowadays in the market we have new devices might reduce the amount of particles in air such as extra-oral suction (EOS). There is some study evaluate the influence of EOS, they found EOS is effective in reducing droplets (9-15). However, most of these study(9-11, 14-16) was perform in vitro on Manikin head and measure particles concentration, that give us some indication of effectiveness of EOS but still it is not precise due to different factors that present in patient mouth such as saliva, blood and infectious agent.

Other study that were done in vitro using Zirc suction -that work as dryshield suction- show efficiency of reduction in aerosol by 88% comparing to other groups(17).

The aim of this study to assess the effectiveness of different dental suction devices that could be contributed to decrease risk of particles count, Bacterial and fungal that arising from patient mouth to indoor air dental clinic

2.2 Rational of research

Most of the previous studies used a low numbers of sample size and the majority of them were conducted in vitro. In addition, they assessed either amount of bacteria or particles comparing EOS to baseline.

In this study, we will analyze particles count and microorganisms comparing EOS to dryshield, combined group and standard group.

2.3 Objective

1. Measure particles, bacteria and fungus that arising from patient's mouth in each group.
2. Evaluate health exposure risk for each group to baseline reading (pre-test).
3. Compare health exposure risk for each group to standard group (Group A)
4. Compare health exposure risk between each of the following groups A, B , C and D.

3. MATERIAL AND METHODS

3.1 Study design

Randomize clinical trial

3.2 Intervention devices

1. Extra oral suction

EOS is used to remove aerosol and droplet that arising from patient mouth and filtering the air.

2. All in one system (dryshield suction)

Dryshied suction is unites of high volume suction and saliva ejection with a bite block, tongue, and oral pathway protection.

3.3 Intervention groups

Group A with high and low suction only (standard care),

Group B using dry shield suction and low section

Group C using extra-oral suction with high and low suction

Group D using dry shield suction and extra-oral suction and low section.

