3.10 Variables and Data collection

Measurement devices

2. Digital dust monitor

Particles matter will be measured using Digital dust monitor (model 3443, KANOMAX.USA INC., made in Japan). This device measure particle size that range from 0.1 to 10 Mm using light scattering method (semiconductor laser radiation light source) with flow rate 1 L/min. air is collect through a filter which is built-in in order to eliminate coarse particles. Filter is reusable and it needs approximately 5 minutes cleaning time depending on environment. Minimum, maximum, and average concentration result show among measurement time. Calibration of device will be performed according to manufacture instruction.

3. Microbial air sampler device (sampl'air ASE)

Is considered as active air sampler method which used to collect microorganism onto solid media with flow rate 100 L/ min. Positive hole conversion table should be used in order to counting colony; colony forming units per volume of air (CFU m⁻³).

In this study a specific agar media will be used to collect oral bacteria and fungus.

Outcome variable

Particle count level (difference in PN count[ΔPN ;post-test – pre-test , counts/ m³])
(continuous variable)

Average of oral bacterial concentration before and during procedure

Average of fungus concentration before and during procedure

Microbial air concentration including bacteria and fungus before and during procedure (floor and near to A.C)

Explanatory variable

Categorical variable

Place ,intervention groups, order of patient ,gender and supragingival calculus (mild, moderate, heavy) ,

Continuous variable

time of procedure that staring from the beginning of scaling until finishing of scaling (in minutes), time on day (morning, afternoon), age, year experience of hygienist, distance of room, humidity, and room temperature.

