3.11 Statistical consideration

All continuous variables will be express as mean and stander deviation

All categorical variables will be described as frequency and percentage

Difference between baseline and during of procedure measurement intended for particle, oral bacteria, fungus and microbial air concentration will be calculating using pairwise t test.

Difference between each categorical groups and particle, oral bacterial, fungus, and microbial air concentration will be tested using two way ANOVA test or one way ANOVA test

Strength and direction of association between particle count levels and time of procedure will be tested using correlation test

Multiple linear regression model will be built to predict particles count level with entrance value of 0.01 and exit value 0.101. Confidence level of 95% will be computed and p-value less than 0.05 will be considered as significant.

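### The four arms form a complete 2×2 of extra-oral suction by intra-oral device, but the ANOVA factors are unnamed and the pre-test reading is not a covariate, so available precision goes unused

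*Combined protocol and SAP*

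**What the plan says.** Section 3.3 gives A high and low suction and B DryShield with low suction. The third arm is listed as "Group C using extra-oral suction with high and low suction"; the fourth, as already the pattern suggests, is "Group D using dry shield suction and extra-oral suction and low section".

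Section 2.3 asks for arm-wise comparisons: objective 3 is "Compare health exposure risk for each group to standard group (Group A") and objective 4 is "Compare health exposure risk between each of the following groups A, B , C and D".

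Section 3.11 states the group analysis in one sentence. Its subject is "Difference between each categorical groups and particle, oral bacterial, fungus, and microbial air concentration". The method follows: these differences, the plan says, "will be tested using two way ANOVA test or one way ANOVA test". It gives no factors, no interaction term and no rule for choosing between the two tests. The categorical variables in section 3.10 are "Place ,intervention groups, order of patient ,gender and supragingival calculus (mild, moderate, heavy"). Treatment is a single variable there, and neither EOS nor intra-oral device is listed separately.

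The pre-test reading enters through the paired before–during test and, for particles, through the outcome itself, which section 3.10 defines as a difference from pre-test. It is not among the explanatory variables for any outcome.

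**The concern.** At least five analyses of treatment fit the ANOVA sentence: one-way on group, or two-way on group with place, order of patient, gender or calculus. EOS by device is a further possibility that the text neither states nor excludes. Naming any factors in advance would stop the model being chosen after the data are seen.

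Naming EOS and device in particular would also yield two estimates from the same patients: what EOS adds averaged over both devices, and how far that addition differs between devices. Using the pre-test reading as a covariate would sharpen every contrast, including the planned pairwise ones, or at worst leave its precision about the same. At stake is precision, not the validity of the planned comparisons.

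**Working it through.** **Structure.** Low suction is constant, so the arms from section 3.3 are four cells:

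| | High suction | DryShield |
|---|---|---|
| No EOS | A | B |
| EOS | C | D |

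**Inputs.** Section 3.7 gives 120 subjects, which matches the abstract's 3 places × 40. Equal allocation (assumed) gives 120/4 = 30 per arm. Section 3.8 can be read as 40 per group, which makes 4 × 40 = 160, so both are shown. The documents give no SD, effect size or power calculation, so no planned power figure can be reproduced. Results are in SD units, with a common SD and independent observations assumed. Alpha is 0.05 (section 3.11), taken as two-sided.

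**Standard errors, n per arm.** A pair such as C−A: √(2/n). Averaged EOS effect, [(C−A)+(D−B)]/2: √(1/n). Interaction, (D−B)−(C−A): √(4/n).

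| | C−A | Averaged EOS | Interaction |
|---|---|---|---|
| SE, n = 30 | 0.258 | 0.183 | 0.365 |
| 95% CI half-width, n = 30 | 0.51 | 0.36 | 0.72 |
| Detectable at 80% power, n = 30 | 0.73 | 0.52 | 1.03 |
| SE, n = 40 | 0.224 | 0.158 | 0.316 |
| Detectable at 80% power, n = 40 | 0.63 | 0.45 | 0.89 |

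Power figures use the noncentral t with 4n−4 degrees of freedom.

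**Power if the EOS effect is the same with both devices, n = 30 (C−A against averaged).** 21% and 37% at 0.3 SD; 48% and 78% at 0.5 SD; 77% and 97% at 0.7 SD. At n = 40 and 0.5 SD: 60% and 88%.

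**Power if it is not the same.** Let the EOS effect be d with high suction and f·d with DryShield. The averaged effect is then d(1+f)/2. It matches C−A for power when (1+f)/2 = 1/√2, so f = √2 − 1 = 0.414. At d = 0.5 and n = 30, where C−A has 48%:

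| f | 1 | 0.75 | 0.5 | 0.25 | 0 |
|---|---|---|---|---|---|
| Averaged | 78% | 66% | 53% | 40% | 27% |

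At f = 0.5 the interaction test has only 10% power.

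**Pre-test adjustment.** Let r be the correlation between the pre-test and during-procedure readings, and k the ratio of their SDs (both assumed).

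- Adjusted against change score (the particle outcome): SE ratio √[(1−r²)/(1+k²−2rk)]. At r = 0.3, 0.5 and 0.7 this is 0.806, 0.866 and 0.922 for k = 1, and 0.979, 1.000 and 0.963 for k = 0.5. The narrowing is about 0–19%.
- Adjusted against an unadjusted during-procedure reading: √(1−r²) = 0.954, 0.866 and 0.714. The narrowing is about 5–29%.

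The same ratio applies to every contrast, so the factor of √2 between C−A and the averaged effect is unchanged. Place uses 2 degrees of freedom and the pre-test reading 1, so the error degrees of freedom at n = 30 fall from 116 to 113.

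**The case against.** The two-way ANOVA may already mean EOS by device. That cannot be excluded, so a reader who inferred that the plan omits or rejects the factorial analysis would go too far; it is simply unspecified.

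A reader might also infer that EOS is the trial's question and that the plan gives up 78% power for 48%. The documents do not support that. The title, and the rationale in section 2.2, read most naturally as arm against arm (EOS with DryShield, with the combination, with standard care), and no objective asks for an averaged effect. The gain from 48% to 78% also requires near-additivity. The documents' one clue points the other way: section 2.1 cites an in vitro aerosol reduction of 88% for a suction said to work like DryShield. If DryShield removed 88% and EOS then removed a fixed share of the remainder, EOS would keep about 12% of its absolute effect. Averaged power at 0.5 SD would be 33% against 48% for C−A at 30 per arm, or 42% against 60% at 40 per arm. This is only an illustration, since the product differs and its comparators are not specified. It does show that both the averaged effect and the interaction depend on the outcome scale: removing a constant share is additive on a log scale but not on a count scale.

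Not every outcome suits this model. The fourth, "Microbial air concentration including bacteria and fungus before and during procedure (floor and near to A.C"), comes from samples that section 3.4 describes as a control for organisms from the air conditioner. An EOS effect on them has doubtful meaning.

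These points limit the claim. What stands is that the factors are unnamed, the pre-test reading is not a covariate, and better use of the data costs little.

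**Conclusion.** The point holds as a cheap improvement, not as an error. The planned comparisons are valid and should remain the main results. The firmest gain is the pre-test adjustment: over the assumed correlations and SD ratios it is no less precise than the alternatives, apart from the 3 degrees of freedom. The averaged EOS contrast has half the variance of C−A under equal allocation and a common SD. It is a mean of two possibly different effects, however, and loses to C−A on power below about 41% retention, so it can only be supportive. The interaction is too imprecise to settle additivity, needing about 1.03 SD for 80% power at 30 per arm. If spread rises with level, as it may for counts, the common-SD figures would not hold on the untransformed scale.

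**What to change.** In section 3.11, replace the ANOVA sentence, for three of the four outcomes, with:

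> For particle count, oral bacteria and fungus, the during-procedure reading, on a scale stated here for each outcome, is modelled with EOS (no: A, B; yes: C, D), intra-oral device (high suction: A, C; DryShield: B, D) and their interaction, adjusting for place and for the pre-test reading on the same scale. The main results are the pairwise differences among A, B, C and D, with 95% CIs. As supportive estimates, with 95% CIs, we report [(C−A)+(D−B)]/2 beside C−A and D−B, and (D−B)−(C−A). A non-significant interaction is not taken as evidence of additivity. No main conclusion rests on the supportive estimates.

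The floor and air-conditioner samples are left out of this model. For particles on the untransformed scale, the group contrasts are the same whether the during-procedure reading or the change from pre-test is the response, once the pre-test reading is a covariate. The outcome definition in section 3.10 is therefore respected.

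The cost is wording only; randomisation and data collection do not change. There are two downsides. First, two supportive estimates are added per outcome: 2 × 3 = 6, beside 6 × 3 = 18 pairwise differences. Second, the pairwise estimates will differ slightly from those of an unadjusted ANOVA, with 3 fewer error degrees of freedom. Without the covariates, the 2×2 model with interaction reproduces the one-way pairwise estimates exactly.

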3.4 Study area and setting

1. This study will be conducted in close rooms at educational hospital, public hospital and private dental clinic. Humidity and temperature will be recorded at the beginning, measuring particles oral bacteria and fungus will be performed 15 minutes before and approximately 15 minutes during scaling and prophylaxes procedure in two opposite quadrants in left side. Additionally 5 minutes will require between two interval to allow cleaning process of filter in Digital dust monitor. Microbial sampler devices will be distributed at several locations in room, three microbial air sampler devices around patient, at 8 o'clock position, 1 o'clock position and 4 o'clock. Another device that will be placed near to air condition and one agar media on the floor to control another microbial agents that could be arising from A.C.. Intervention devices that will be used is EOS where being place on left side of patent to allow comfortable movement of hygienist and suction cone will be away from patient mouth from 10 -15 cm based on manufacture instruction.

3.5 Assessment

Risk

Noise that will be caused by dental suction and other measurement devices.

patient could spend additional time in dental clinic before procedure starting

Benefit

Experience more comfortable treatment setting than routine setting

Alternative

Subjects have all rights to withdraw from study at any time for any reasons. In addition, scaling and prophylaxis treatment will be completed as usual.

3.6 Study participants

Patients from King Abdulaziz dental hospital, dental private office, and King Fahad hospital

3.7 Sample size

Total sample will be 120 subjects.

3.8 Sampling technique

Multiple stage stratified random sampling at place level then subject randomly assign from schedule appointment using simple random sampling. Last stage, Simple random sampling of 40 subject at each 4 groups using computer-generated random numbers.

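### Section 3.8 reads as 40 subjects in each of four groups (160), against a total of 120 in section 3.7 and the abstract; no section gives a group size that fits 120

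*Combined protocol and SAP*

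**What the plan says.** All the relevant statements are in the current text of the combined protocol and SAP.

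- **Total.** Section 3.7 consists of one sentence: "Total sample will be 120 subjects".
- **Places.** The abstract says the trial "will be conducted in three different places: educational hospital, public hospital, and private clinic". Section 3.4 names the same three settings.
- **Number per place.** The abstract adds: "In each place 40 subject will be recruited".
- **Groups.** The abstract states "In this study will be compared between four intervention groups", and section 3.3 lists them as A to D.
- **Allocation.** Section 3.8 sets out stages: stratification by place, selection of subjects from the appointment schedule, and finally "Simple random sampling of 40 subject at each 4 groups using computer-generated random numbers".

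No section gives an allocation ratio, a number per group that is consistent with 120, a dropout allowance, or a power calculation.

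**The concern.** Section 3.8 is the only section that describes how subjects are assigned to groups, and the only one that puts a number beside the groups. That number does not fit the total in the section just before it.

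Group size matters here because the trial exists to compare the groups. One of the objectives in section 2.3 is to "Compare health exposure risk between each of the following groups", A to D, and section 3.11 plans ANOVA for that purpose. As the plan stands, a reader cannot tell how many subjects each group will have. Someone preparing the random list from section 3.8 could build 160 slots, while recruitment under section 3.7 stops at 120. A trial that enrols its full 120 is complete against section 3.7 and looks a quarter short against section 3.8.

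**Working it through.** **Inputs**

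| Quantity | Value | Source |
|---|---|---|
| Total | 120 | Section 3.7 |
| Places | 3 | Abstract; section 3.4 |
| Subjects per place | 40 | Abstract |
| Groups | 4 | Abstract; section 3.3 |
| Number set beside the groups | 40 | Section 3.8 |
| Allocation ratio, dropout, power, effect size, SD | not stated | – |

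**1. Reproduce the stated total.** Places × subjects per place = 3 × 40 = 120. This agrees with section 3.7.

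**2. Apply section 3.8 as worded.** Groups × 40 = 4 × 40 = 160. This does not agree with 120.

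- Excess: 160 − 120 = 40 subjects; 40/120 = 33% above the stated total.
- Equivalently, 120 is 40/160 = 25% below 160.

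**3. Apply the same wording within each place**, since section 3.8 starts by stratifying on place. 3 × 4 × 40 = 480. This does not agree either.

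**4. Ask where the 40 fits.** 120/40 = 3, which is the number of places. The number of groups is 4.

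**5. Test whether 40 per group can be laid over three equal places.** 160/3 = 53.3 per place, which is not a whole number and not the 40 in the abstract. 40/3 = 13.3 per group per place, also not a whole number.

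**6. Look for a bridge between 120 and 160.** A dropout rate of 25% would turn 120 into 120/(1 − 0.25) = 160, but the documents state no dropout rate, so this cannot be the explanation.

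**7. Group size implied by 120.** Assuming equal groups: 120/4 = 30 per group, or 40/4 = 10 per group per place. Check: 10 × 4 × 3 = 120.

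**8. What the difference means for precision (illustration only).** The plan gives no power inputs. I assume a two-sided 0.05 level, 80% power, one pairwise comparison and no multiplicity adjustment. The detectable standardised difference is then (1.960 + 0.842) × √(2/n):

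- n = 30 per group: about 0.72 SD
- n = 40 per group: about 0.63 SD

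**The case against.** The strongest reply is that 160 is only one expansion of an ungrammatical sentence. Section 3.8 lists stages in order, starting with place. At the last stage each place has 40 subjects, so the sentence can be taken to mean that the 40 at each place are randomised over the four groups. That gives 3 × 40 = 120. The total itself is stated outright in section 3.7, and no section states 160. On this view the defect is unclear wording, and a reader would have to overlook section 3.7 to conclude that the trial is under-recruited.

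Much of this stands. The reading is the most likely intent, and 120 is the better-supported total. But it needs words that the sentence does not contain: the last stage names no place, and the only unit beside the 40 is the groups. Accepting 120 also does not produce a group size, because none that fits is stated. The sentence needs correcting under either reading.

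Two further points are fair. First, the missing group size is an omission separate from the conflicting count; it would remain if section 3.8 were merely reworded to fit 120, so the correction should deal with both. Second, randomising each subject independently would not guarantee exactly 10 per group per place. A random draw to fixed group sizes within place would, and that is compatible with the simple random sampling named in section 3.8, but the text should say so.

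**Conclusion.** The concern holds. As written, section 3.8 gives a count of 160 that disagrees with the 120 in section 3.7 and in the abstract, a gap of 40 subjects or 33% of the stated total. The likely cause is that the per-place number was attached to the groups. If so, the group size is 30 and not 40; this rests on 120 being the intended total and on equal groups, neither of which section 3.8 states.

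This should be fixed, but its reach is limited. The total and the per-place number agree with each other, and the 40 enters no power calculation or planned test, so no power claim fails and the design is not invalidated. Confidence in the inconsistency is high, because it follows from the stated counts alone.

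**What to change.** Ask the sponsor to confirm three things: that 120 is the intended total, whether the four groups are meant to be equal, and whether group sizes are fixed within each place. Then correct the text accordingly.

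- **If 120 and equal groups:** restate the last stage of section 3.8, for example: *At each of the three places, 40 subjects are allocated at random to groups A to D using computer-generated random numbers, with group sizes fixed at 10 per group per place, giving 30 per group and 120 in total.*
- **If 120 and unequal groups:** state four group numbers that sum to 120, and how each is spread over the places.
- **If 160:** correct section 3.7 and the abstract instead, and state the number for each place. These numbers cannot be equal, because 160 is not divisible by three.

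In the first two cases the cost is a sentence or so of protocol wording and no change in enrolment; the stated number beside the groups changes to one that sums to 120. In the third, enrolment rises by 40 subjects over the current total.

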3.13 Limitation and strength

Randomly involved of subject into intervention groups is one of strength in our study. One of limitation is subject and observer could not be blind.

4. Devices and setting figure

[figure not shown]
Name	Picture
a) High volume suction	
b) Low volume suction	
All in one system (dry-shield)	
Extra oral suction	
Microbial air sampler device (sampl'air ASE)	

**Digital dust monitor , KANOMAX , model
3443,**

**Circles represent location of microbial air
sampler device**

**Square represents digital dust monitor
device**

5. References

2. Garner JS. Guideline for isolation precautions in hospitals. The Hospital Infection Control Practices Advisory Committee. *Infection control and hospital epidemiology*. 1996;17(1):53-80.

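### The last allocation stage reads as 40 per group (160 in all) against a stated total of 120, and names no restriction that keeps group sizes equal within place

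*Combined protocol and SAP*

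**What the plan says.** The abstract of the combined protocol and SAP names "three different places: educational hospital, public hospital, and private clinic" and states "In each place 40 subject will be recruited". It describes four groups, A to D. Section 3.7 gives the overall size: "Total sample will be 120 subjects".

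Section 3.8 describes the early stages as "Multiple stage stratified random sampling at place level then subject randomly assign from schedule appointment using simple random sampling". The final stage is "Simple random sampling of 40 subject at each 4 groups using computer-generated random numbers".

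No section gives a group size of 30, a cell size of 10, an allocation ratio, a block size or a concealment method. Section 3.10 lists place among the explanatory variables. Section 3.11 allows either a one-way or a two-way ANOVA for the group comparisons, and does not say that place is the second factor. Section 3.13 adds "One of limitation is subject and observer could not be blind".

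**The concern.** Two things in the last stage need attention.

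First, the count. The only number attached to the groups is 40, and four groups of 40 do not fit a trial of 120. Whoever generates the list must decide whether to follow section 3.8 or section 3.7.

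Second, the method. Stratifying by place balances the groups within place only if the allocation inside each stratum is restricted in some way. Simple random allocation inside a stratum is not. Objectives 3 and 4 in section 2.3 call for each group against A and for all groups against one another, so all six pairs matter and the least favoured pair is of interest. Small cells weaken a two-way analysis by place and group. If the one-way option is used, chance differences in place mix between groups go unadjusted.

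**Working it through.** **Inputs.** Places: 3, with 40 subjects each (abstract). Groups: 4 (abstract and section 3.3). Total: 120 (section 3.7). Two-sided 5% significance is assumed, since section 3.11 gives 0.05 without sidedness. The documents give no effect size, SD or power, so the 120 can be checked only as a count.

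**1. The count.**
- By place: 3 × 40 = 120. This reproduces section 3.7.
- By group, as section 3.8 is worded: 4 × 40 = 160. This does not. Nor can 160 be split equally over three places (160/3 = 53.3).
- Equal allocation of 120 implies 120/4 = 30 per group and 40/4 = 10 per place-by-group cell. Neither figure is stated.

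**2. Imbalance if the last stage means independent draws with probability 1/4.**
- Cell size: mean 40 × 0.25 = 10, SD √(40 × 0.25 × 0.75) = 2.74, 95% range 5 to 16.
- Group total: mean 120 × 0.25 = 30, SD √(120 × 0.25 × 0.75) = 4.74, 95% range 21 to 40.
- Chance that one place splits 10/10/10/10: 40!/(10!⁴ × 4⁴⁰) = 0.39%.
- From 200,000 simulated allocations (three places of 40):

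| Event | Result |
|---|---|
| At least one of 12 cells has 6 or fewer | 75% |
| At least one of 12 cells has 5 or fewer | 43% |
| Smallest group has 24 or fewer | 46% |
| Largest minus smallest group, median | 11 |

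**3. Imbalance if the last stage means a fixed-size draw.** Dividing each place's 40 into four equal draws gives 10 per cell and no imbalance. The figures in step 2 then do not apply.

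**4. Precision under independent draws.** In an additive place + group model, the information matrix for the groups is I = diag(group totals) − Σ over places of (n nᵀ)/40, where n is the vector of four cell counts in a place. The variance of a pairwise contrast c is cᵀI⁻c (generalised inverse) times σ². With equal cells it is 2σ²/30. Relative to that, by simulation:
- average over allocations: +4.5%
- worst-hit of the six pairs: +16% (median), +34% (95th percentile)

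**5. Power.** The effect with 80% power at 30 v 30 is √(2/30) × (1.960 + 0.842) = 0.72 SD (an assumed reference, not a protocol figure). Averaged over the allocations, power for one place-adjusted contrast is about 78%. For a pair whose variance is up 16%, it is Φ(2.802/√1.16 − 1.960) = 74%. At 34% it is Φ(2.802/√1.34 − 1.960) = 68%.

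**6. Predictability of a restricted list.** The table gives the expected share of assignments guessed correctly by someone who knows all earlier ones. For blocks of 4 it is (1/4 + 1/3 + 1/2 + 1)/4 = 52%.

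| List | Correct guesses |
|---|---|
| Simple randomisation | 25% |
| One permutation of 40 per place | 37% |
| Fixed blocks of 8 | 47% |
| Fixed blocks of 4 | 52% |

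**7. Do freely varying blocks of 4 and 8 reach 40?** With equal-probability sizes, let p(k) be the chance that the list stops exactly at 4k subjects. Then p(k) = ½p(k−1) + ½p(k−2), with p(0) = 1 and p(1) = ½, so p(10) = 0.67. For all three places the chance is 0.67³ = 0.30. Otherwise a block of 8 is cut off and equal cells are not assured, so the block sizes must be constrained to sum to 40.

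**The case against.** The strongest reply is that simple random sampling with a number attached ordinarily means a fixed-size draw. On that view the 40 could be a place's subjects shared over four groups, which agrees with 120 and yields equal cells. This stands as a fair reading, and every imbalance figure above is conditional on the other one. It does not rescue the sentence, which attaches 40 to the groups and nowhere gives 10 or 30.

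A second reply is that the statistical loss is modest. That also stands. The average loss is about 2 power points. The worst-pair and any-cell figures are extremes over 6 pairs and 12 cells. Cells of 5 or 6 can still be analysed: a cell of 2 or fewer occurs in about 1% of allocations.

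Third, a reader might infer that unequal places bias the group comparisons. The documents do not support this. Under randomisation a chance imbalance costs precision but does not bias the comparison, and one-way ANOVA keeps its error rate. The particle outcome in section 3.10 is a change from the pre-procedure reading, which removes additive background differences between places. A reader might likewise take place to be the strongest nuisance factor, but section 3.10 lists it beside calculus, procedure time, hygienist experience and humidity without ranking them.

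Finally, restricted allocation is not free of drawbacks. The trial is unblinded and no concealment is described, so a more predictable list could let enrolment be influenced.

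**Conclusion.** The concern holds in a limited form. The last stage is wrong as written, because 160 by its wording conflicts with 120 in section 3.7 and with 3 × 40 in the abstract. It also leaves open whether group sizes are held equal within place. That part rests on the documents alone.

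The imbalance and its cost in precision rest on assuming independent 1:1:1:1 draws, and the precision figures also on an additive place + group model. On those assumptions unequal cells are nearly certain, but the average loss is small and the real exposure is an unlucky pair or a sparse cell.

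It would go too far to say that the plan chose a method that must leave the groups unequal, since a fixed-size draw would not. It would also go too far to say that blocking guarantees balance at no cost. Blocks must be made to total 40, section 3.5 allows subjects to withdraw so the analysed cells can still differ, and predictability rises.

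**What to change.** Replace the last stage in section 3.8 with wording such as:

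> Within each place, 40 subjects are allocated 1:1:1:1 by a computer-generated restricted list constrained to total exactly 40 (one random permutation of 10 per group, or randomly ordered blocks of 4 and 8 summing to 40). This gives 10 per group per place, 30 per group and 120 in total. Each assignment is concealed until the subject is enrolled.

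The sponsor should choose one of the two list types. The single permutation is the less predictable when set against fixed blocks of 4 or 8. State in section 3.11 that place is a factor in every group comparison, so that a one-way ANOVA ignoring place is no longer an option for those comparisons.

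The cost is a new list, a few sentences of protocol text and a concealment procedure such as sealed or central assignment. No extra subjects are needed.
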